2.8.4 Subgroup analyses

Subgroup analyses of the primary efficacy endpoint will be performed to assess the homogeneity of the treatment effect across the following subgroups (categories with fewer than 5 participants may be combined with other categories). Descriptive statistics will be provided.

- Age (<30, \geq 30 years)
- Gender (Male, Female)
- Baseline Hurley Stage (Hurley Stage II, Hurley Stage III)
- BMI (<25, 25 to 30, \geq 30 Kg/m²)
- Smoking status (Current smoker, Former smoker, Never smoker)
- Disease duration (<10, \geq 10 years)

2.9 INTERIM ANALYSES

No interim analysis is planned.

2.10 CHANGES TO PROTOCOL-PLANNED ANALYSES

This section summarizes major statistical changes to protocol-planned analysis.

Table 9 - Major statistical changes to protocol-planned analyses

Section # and Name	Description of Change	Rationale
Section 1.2 Objectives and endpoints	Exploratory endpoint changed from "Percentage of participants who experience 5-point reduction in DLQI at Weeks 16 and 28 among participants with Baseline DLQI \geq 4" to "Percentage of participants who experience 4-point reduction in DLQI at Weeks 16 and 28 among participants with Baseline DLQI \geq 4"	ACT16852 Protocol section 8.2.2.3 on the DLQI claims that "A 4-point change in the DLQI score (DLQI response) has been reported to be meaningful for the participant.

3 SAMPLE SIZE DETERMINATION

Data from historical studies which have similar target population and study design will be used as prior information supplementing the placebo arm, using a Bayesian approach. A prior distribution of the percentage of participants that achieved HiSCR50 at Week 16 of the placebo arm was determined based on the data observed in the historical studies (1).

For the biologic and small molecule immunosuppressive-naïve population, an informative prior distribution for the placebo group HiSCR50 rate has been chosen as a beta distribution with parameter (█). This prior distribution contributes an approximate effective sample size of █ participants for the placebo treatment group. Sample size calculations were performed to ensure reasonable accuracy for the estimation of the response rate. █
█
█

Table 10 - Accuracy of the 80% credible interval in the Biologic and small molecule immunosuppressive-naïve population

SAR442970 incidence rate (n)	Placebo rate (n)	Lower limit	Upper limit	Half-width
█	█	█	█	█

A sample size of █ participants randomized in a 2:1 ratio to SAR442970 versus placebo will provide a half-width for the 80% credible interval of less than █ which is deemed sufficient.

Table 11 - Accuracy of the 80% credible interval in the TNF-experienced population

SAR442970 incidence rate (n)	Placebo rate (n)	Lower limit	Upper limit	Half-width
█	█	█	█	█

For TNF-experienced population, an informative prior distribution for the placebo group HiSCR50 rate has been chosen as a beta distribution with parameter (█). This prior distribution contributes an approximate effective sample size of 2 participants for the placebo treatment group. Sample size calculations were performed to ensure reasonable accuracy for the estimation of the response rate. █
█

A sample size of 18 participants randomized in a █ ratio to SAR442970 versus placebo will provide a half-width for the 80% credible interval of less than █ which is deemed sufficient.

4 SUPPORTING DOCUMENTATION

4.1 APPENDIX 1 LIST OF ABBREVIATIONS

ACPA:	Anti-Citrullinated Protein Antibodies
ADA:	Anti-drug antibody, Anti-drug antibodies
AE:	adverse event
AESIs:	Adverse event of special interest
ALT:	Alanine aminotransferase
ANCOVA:	analysis of covariance
ASCA:	Anti-Saccharomyces Cerevisiae Antibodies
AST:	Aspartate aminotransferase
CMH:	Cochran-Mantel-Haenszel
CRP:	C-Reactive protein
CXCL13:	C-X-C Motif Chemokine Ligand 13
DLQI:	Dermatology Life Quality index
ECG:	electrocardiogram
EOS:	End of study, End of study
EOT:	End of treatment
ESR:	Erythrocyte Sedimentation Rate
HiSCR:	Hidradenitis Suppurativa Clinical Response
HiSQOL:	Hidradenitis Suppurativa Quality Of Life
HS:	Hidradenitis suppurativa
hsCRP:	High-Sensitivity C-Reactive Protein
IEs:	Intercurrent events
IHS4:	International Hidradenitis Suppurativa Severity Score

IL-6:	Interleukin-6
IMP:	investigational medicinal product
ITT:	Intent-to-treat
LLOQ:	Lower limit of quantification
MedDRA:	Medical Dictionary for Regulatory Activities
MedDRA:	medical dictionary for regulatory activities
MMRM:	Mixed effect model with repeated measures
NRS:	Numeric rating scale
OX40L:	Soluble OX40 Ligand
PCSA:	Potentially clinically significant abnormality
PCSA:	potentially clinically significant abnormality
PK:	Pharmacokinetics
PT:	preferred term
REML:	Restricted Maximum Likelihood
SAA:	Serum Amyloid A
SAEs:	Serious adverse events
SD:	standard deviation
SOC:	system organ class
TE:	treatment-emergent, treatment-emergent
TEAE:	treatment-emergent adverse event
TEAEs:	Treatment-emergent adverse events

WHO-DD:	World Health Organization-drug dictionary
WOCF:	Worst observation carried forward

4.2 APPENDIX 2 PARTICIPANT DISPOSITIONS

The number (%) of participants included in each of the analysis populations listed in [Table 4](#) will be provided.

Screen failures are defined as participants who consent to participate in the study but are not subsequently randomized. The number (%) of screen failures and reasons for screen failures will be provided in the screened population.

Period A:

The number (%) of participants in the following categories will be provided:

- Randomized participants
- Randomized but not exposed participants
- Randomized and exposed participants
- Participants who completed Treatment Period A as per protocol
- Participants who did not complete the Treatment Period A as per protocol and main reason for permanent intervention discontinuation

Period B:

The number (%) of participants in the following categories will be provided:

- Enrolled participants
- Enrolled but not exposed participants
- Enrolled and exposed participants
- Participants who completed Treatment Period B as per protocol
- Participants who did not complete Treatment Period B as per protocol and main reason for permanent intervention discontinuation
- Vital status at last study contact

Listings of participants with permanent study intervention discontinuation or with premature end of study (i.e., who did not complete the study period as per protocol) will be provided for the safety population along with the main reason of discontinuations.

In addition, the number (%) of participants screened, screened-failed, randomized, with permanent intervention discontinuation in Period A, with permanent study intervention discontinuation in Period B, and with early study discontinuation will be provided by country and site.

Protocol deviations

Critical or major protocol deviations (automatic or manual) will be summarized in the randomized population.

4.3 APPENDIX 3 DEMOGRAPHICS AND BASELINE CHARACTERISTICS, PRIOR OR CONCOMITANT MEDICATIONS

Demographics and baseline characteristics, medical and surgical history

The following demographics and baseline characteristics, medical and surgical history and disease characteristics at baseline will be summarized using descriptive statistics in the randomized population.

Demographics and baseline characteristics:

Provided for safety population, and other analyses populations if deemed necessary,

- Age in years as quantitative variable and in categories (<18, ≥ 18 - <40, ≥ 40 - <60, ≥ 60 - ≤ 70)
- Gender (Male, Female)
- Race (White, Black or African American, Asian, Native Hawaiian or Other Pacific Islander, American Indian or Alaska Native, Multiple, Unknown, Not Reported)
- Ethnicity (Hispanic or Latino, not Hispanic or Latino, Unknown, Not Reported)
- Region (**Western Countries**: Australia, Belgium, Canada, Denmark, France, Germany, Greece, Italy, Netherlands, Spain, Sweden, USA; **Eastern Europe**: Poland, Czech Republic; **Latin America**: Chile)
- Body weight as quantitative variable (kg) and in categories (< 90; ≥ 90 kg)
- Body mass index (BMI) as quantitative variable (kg/m²) and in categories (<25; ≥ 25 - <30; ≥ 30 - < 35; ≥ 35 kg/m²)
- Smoking habit (Never; Former; Current)

Baseline safety and efficacy parameters (apart from those listed above) will be presented along with the safety and efficacy summaries.

Disease characteristics at baseline

Provided for efficacy population,

- Time since diagnosis of the disease (years)
- Age at diagnosis of disease as quantitative variable (years) and in categories (< 18, ≥ 18 - < 40, ≥ 40 - < 60, ≥ 60 - ≤ 70 years)

- HS treatment history (biologic and small molecule immunosuppressive-naïve, TNF-experienced)
- Baseline lesion counts (by lesion type)
- Baseline Hurley stage (II, III)
- Baseline C-reactive protein
- Concomitant antibiotic therapy (yes, no)

Medical and surgical history

Medical and surgical history includes Alcohol, Nicotine, Substance usage, significant medical or surgical events (including tonsillectomy and history of hypertension and/or diabetes). Medical and surgical history will be coded to a LLT, PT, HLT, HLGT and associated primary SOC using the MedDRA version currently in effect at Sanofi at the time of database lock. All medical and surgical history will be summarized by primary SOC and PT using a frequency table (number and % of participants) by study intervention group.

Prior or concomitant medications

All medications will be coded using the World Health Organization-Drug Dictionary (WHO-DD) using the version currently in effect at Sanofi at the time of database lock.

- Prior medications are those the participant received prior to first double-blinded IMP intake. Prior medications can be discontinued before first administration or can be ongoing during treatment period.
- Concomitant medications are any medications received by the participant concomitantly to the IMP during the TE period.
- Post-treatment medications are those the participant received in the period running from the end of the concomitant medications period up to the end of the study.
- A given medication can be classified as a prior medication and/or as a concomitant medication and/or as post-treatment medication. If it cannot be determined whether a given medication was taken prior or concomitantly or post, it will be considered as prior, concomitant, and post-treatment medication.

The prior medications and concomitant medication will be summarized for the randomized population. Participants will be counted once in each ATC category (anatomic or therapeutic) linked to the medications. Concomitant medication will be presented for Period A and Period B separately.

Medications will be summarized by intervention group according to the WHO-DD dictionary, considering the first digit of the anatomic category (ATC) class (anatomic category) and the first 3 digits of the ATC class (therapeutic category). All ATC codes corresponding to a medication will be summarized, and participants will be counted once in each ATC category (anatomic or therapeutic) linked to the medication. Therefore, participants may be counted several times for the same medication.

The tables for prior medications will be sorted by decreasing frequency of ATC followed by all other therapeutic classes based on the overall incidence across intervention groups. In case of equal frequency regarding ATCs (anatomic or therapeutic categories), alphabetical order will be used.

The tables for concomitant medications will be sorted by decreasing frequency of ATC followed by all other therapeutic classes based on the incidence in the SAR442970 group in Period A or on the incidence in the overall group in Period B. In case of equal frequency regarding ATCs (anatomic or therapeutic categories), alphabetical order will be used.

4.4 APPENDIX 4 DATA HANDLING CONVENTIONS

Demographic formulas

- Age at onset of HS (years):
 - Year of first diagnosis of HS- Year of birth
- Time since first diagnosis of HS (years):
 - $(\text{Year of randomization} - \text{Year of first diagnosis of HS}) + (\text{Month of randomization} - \text{Month of first diagnosis of HS})/12$ if at least year and month are available
 - or
 - $(\text{Year of randomization} - \text{Year of first diagnosis of HS})$ if only year is available

Unscheduled visits

Unscheduled visit measurements of efficacy, laboratory data, vital signs, ECG and biomarkers and ADA will be used, in particular for computation of baseline, the last on-treatment value, analysis according to PCSAs, and the shift summaries for safety. They will also be included in the by-visit summaries if they are re-allocated to scheduled visits.

Biomarkers

- The baseline biomarker parameter is defined as the last non-missing value prior to the first IMP dose of IMP unless otherwise specified.
- Imputation of censored values: If any value below the lower limit of quantitation (LLOQ) is found, the values <LLOQ will be reported in tables and the associated values will be imputed by LLOQ/2 for data plotting and computation of summary statistics. If any value above the upper limit of quantitation (ULOQ) is found, the number of values >ULOQ will be reported in tables and the associated values will be imputed by the ULOQ for data plotting and computation of summary statistics. If the unit is %, the values >ULOQ will be imputed by $(100+\text{ULOQ})/2$, instead of ULOQ. Whenever possible, the value of the LLOQ and ULOQ should be displayed in plots of absolute values, whereas it is not possible when plotting percent changes from baseline. If the value of any summary statistics will be itself <LLOQ (>ULOQ, respectively), it will not be reported as such but shown as 'BLOQ' ('ALOQ', respectively).

- Change and Percent change: For biomarkers, the change and the percent change from baseline are reported in addition to the analysis values. The percent change from baseline is defined as $100 \times \frac{X-B}{B}$, with X the analysis value at a given timepoint and B the baseline analysis value for the same participant. The change from baseline is defined as $X - B$.

Analysis windows for time points

The following analysis windows will decide how the scheduled and/or unscheduled visits will be used in the by-visit analyses of efficacy, safety, PK and ADA variables.

A measurement (scheduled or unscheduled) will be used if it is available and measurement date is within the analysis window.

After applying these time windows, if multiple assessments are associated to the same time point, the closest from the targeted study day will be used. If the difference is a tie, the value after the targeted study day will be used. If multiple valid values exist within a same day, then the first value of the day will be selected. For procedures planned on Visit 2, if it is done on the same date as the first IMP injection but the performance time is missing, it will belong to the Visit 2 window.

If there is no measurement for a given parameter in an analysis window, data will be considered missing for the corresponding visit.

Table 12 - Analysis window definition for safety analysis

Analysis visits	Targeted study day ^a	Time window				
		Vital signs	Fasting lipid panel	Non-fasting laboratory tests	Urinalysis	12-lead ECG
Period A						
Screening	-28 to -14	<-14	<-14	<-14	<-14	<-14
Baseline	1	-14 - 1	-14 - 1	-14 - 1	-14 - 1	-14 - 1
Week 2	15	2 - 21	2 - 21	2 - 21	2 - 21	2 - 21
Week 4	29	22 - 35	22 - 35	22 - 35	22 - 35	22 - 35
Week 6	43	36 - 49	36 - 49	36 - 49	36 - 49	36 - 49
Week 8	57	50 - 63	50 - 63	50 - 63	50 - 63	50 - 63
Week 10	71	64 - 77	64 - 77	64 - 77	64 - 77	64 - 77
Week 12	85	78 - 91	78 - 91	78 - 91	78 - 91	78 - 91
Week 14	99	92 - 105	92 - 105	92 - 105	92 - 105	92 - 105
Week 16	113	106 - D ^b	106 - D ^b	106 - D ^b	106 - D ^b	106 - D ^b
Period B						
Week 18	15	2 - 21	2 - 21	2 - 21	2 - 21	2 - 21
Week 20	29	22 - 35	22 - 35	22 - 35	22 - 35	22 - 35
Week 22	43	36 - 49	36 - 49	36 - 49	36 - 49	36 - 49
Week 24	57	50 - 63	50 - 63	50 - 63	50 - 63	50 - 63
Week 26	71	64 - 77	64 - 77	64 - 77	64 - 77	64 - 77
Week 28	85	78 - 112	78 - 112	78 - 112	78 - 112	78 - 112
Week 36	141	>112	>112	>112	>112	>112

a Day 1 in Period A is the day of the first blinded IMP administration (or the day of randomization for participant not exposed).

Day 1 in Period B is the day of the first open-label IMP administration.

b Last window in Period A is the 1st dose of open-label IMP administration.

Table 13 - Analysis window definition for efficacy endpoints

Analysis visit	Targeted study day ^a	Time windows			
		HS clinical parameters	Dermatology Life Quality Index	Hidradenitis Suppurativa Quality of Life	
Period A					
Screening	-28 to -14	<-14	<-14		<-14
Baseline	1	-14 - 1	-14 - 1		-14 - 1
Week 2	15	2 - 21	2 - 21		2 - 21
Week 4	29	22 - 42	22 - 42		22 - 42
Week 6	43				
Week 8	57	43 - 70	43 - 70		43 - 70
Week 10	71				
Week 12	85	71 - 98	71 - 98		71 - 98
Week 14	99				
Week 16	113	99 - D ^b	99 - D ^b		99 - D ^b
Period B					
Week 18	15				
Week 20	29	2 - 42	2 - 42		2 - 42
Week 22	43				
Week 24	57	43 - 70	43 - 70		43 - 70
Week 26	71				
Week 28	85	>70	>70		>70

^a Day 1 in Period A is the day of the first blinded IMP administration (or the day of randomization for participant not exposed). Day 1 in Period B is the day of the first open-label IMP administration.

^b Last window in Period A is the 1st dose of open-label IMP administration.

Table 14 - Analysis window definition for daily questionnaires

Analysis visit	Targeted study day ^a	Time windows		
		Daily Diary HS-Skin Pain NRS	Daily Diary PP-NRS	Daily diary analgesic use
Period A				
Screening	-28 to -7	<-7	<-7	<-7
Baseline	1	-7 - <1	-7 - <1	-7 - <1
Week 2	15	8 - 14	8 - 14	8 - 14
Week 4	29	22 - 28	22 - 28	22 - 28
Week 6	43	36 - 42	36 - 42	36 - 42
Week 8	57	50 - 56	50 - 56	50 - 56
Week 10	71	64 - 70	64 - 70	64 - 70
Week 12	85	78 - 84	78 - 84	78 - 84
Week 14	99	92 - 98	92 - 98	92 - 98
Week 16	113	106 - D ^b	106 - D ^b	106 - D ^b
Period B				
Week 18	15	8 - 14	8 - 14	8 - 14
Week 20	29	22 - 28	22 - 28	22 - 28
Week 22	43	36 - 42	36 - 42	36 - 42
Week 24	57	50 - 56	50 - 56	50 - 56
Week 26	71	64 - 70	64 - 70	64 - 70
Week 28	85	78 - 84	78 - 84	78 - 84

a Day 1 in Period A is the day of the first blinded IMP administration (or the day of randomization for participant not exposed). Day 1 in Period B is the day of the first open-label IMP administration.

b D = minimum (Day 112, the day prior to the first open-label IMP)

Table 15 - Analysis windows for pharmacokinetics/pharmacodynamics variables

Analysis visit	Targeted study day ^a	Time windows				
		ADA	Blood biomarkers	PK	PD Biomarker	Skin Biopsy
Period A						
Screening	-28 to -14	<-14	<-14		<-14	
Baseline	1	-14 - 1	-14 - 1	≤1	-14 - 1	≤1
Week 2	15	2 - 21	2 - 21		2 - 21	
Week 4	29	22 - 42	22 - 42	2 - 49	22 - 42	
Week 6	43					
Week 8	57	43 - 70	43 - 70	50 - 63	43 - 70	
Week 10	71			64 - 77		
Week 12	85	71 - 98	71 - 98	78 - 98	71 - 98	
Week 14	99					
Week 16	113	99 - D ^b	> 1			
Period B						
Week 18	15			2 - 21		
Week 20	29	2 - 42	2 - 42	22 - 70	2 - 42	
Week 22	43					
Week 24	57	43 - 70	43 - 70		43 - 70	
Week 26	71					
Week 28	85	71 - 112	> 70	71 - 112	71 - 112	
Week 36	141	> 112		> 112	> 112	

a Day 1 in Period A is the day of the first blinded IMP administration (or the day of randomization for participant not exposed). Day 1 in Period B is the day of the first open-label IMP administration.

b Last window in Period A is the 1st dose of open-label IMP administration.

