### Overall design synopsis:

This is a multinational, multi-center, randomized, double-blind, placebo-controlled, Phase 2a proof of concept study to evaluate the efficacy and safety of SAR442970 in adult participants with moderate to severe HS.

The intervention in the study includes investigational medicinal product (IMP) administration every 2 weeks (Q2W) to complete 28 weeks of treatment with SAR442970. The study is

composed of 3 parts: a double-blind, placebo-controlled period (Period A), followed by an open-label period (Period B), and then followed by a safety Follow-up Period (Period C).

Participants will receive SAR442970 150 milligrams (mg) or matching placebo Q2W at the Week 0 visit up to the Week 14 visit as part of Period A, the double-blind, placebo-controlled period. Beginning at the Week 16 visit, all participants will receive SAR442970 150 mg Q2W up to the visit prior to the individual participant's end of treatment (EOT) visit as part of Period B, the open-label period. Period C will be an 8-week safety Follow-up Period commencing with the End of Treatment (EOT) visit and concluding with the End of Study (EOS) visit. Participants will not be expected to receive more than 14 doses of SAR442970. [For participants in the US, response will be assessed at the Week 20 visit (see definition of response in [Section 4.1](#)). Responders at Week 20 will continue in Period B to complete the 12-week open-label period. Non-responders at Week 20 will move directly to the safety follow-up period (Period C) with the Week 20 visit serving as their EOT visit. No IMP will be administered to non-responders at their EOT visit at Week 20].

The target population of the study is participants with HS based on a history of signs and symptoms consistent with HS for at least 1 year prior to Baseline and demonstrating moderate to severe disease at Baseline as defined by HS lesions present in at least 2 distinct anatomic areas (eg, left and right axilla; or left axilla and left inguino-crural fold), one of which must be Hurley Stage II or Hurley Stage III, an abscess and inflammatory nodule (AN) count of  $\geq 3$ , a draining tunnel count  $\leq 20$ , and C-reactive protein (CRP) level of  $> 3$  mg/L.

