### **Brief summary:**

This is a multinational, multi-center, randomized, double-blind, placebo-controlled, Phase 2 study. The purpose of the present study is to measure efficacy, safety, PK, and biological effects of treatment with SAR442970 compared with placebo in adult participants with moderate to severe HS.

Study details include the following:

- The study duration will be up to 40 weeks. For US participants who are non-responders at the Week 20 assessment, the study duration will be 28 weeks.
- The treatment duration will be up to 28 weeks. Participants will receive SAR442970 150 mg or matching placebo Q2W beginning at the Week 0 visit up to the Week 14 visit as part of Period A, the double-blind, placebo-controlled period. Beginning at the Week 16 visit, all participants will receive SAR442970 150 mg Q2W up to the visit prior to the individual participant's EOT visit as part of Period B, the open-label period. For US participants, response will be assessed at the Week 20 visit. Responders at Week 20 will continue in Period B to complete the 12-week open-label period. Non-responders at Week 20 will move directly to the safety follow-up period with the Week 20 visit serving as their EOT visit.
- The number of visits will be at maximum 17.

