Following repeated SC administration, SAR442970 median  $T_{max}$  occurred at approximately 72 hours (3 days) post-dose; however, the next sampling time-point was at 168 hours so potentially the true  $T_{max}$  was in that range. The  $T_{max}$  was followed by a monophasic decline in serum concentrations, with a  $t_{1/2}$  ranging from 170 to 212 hours (7 to 9 days). Exposure based on  $AUC_{0-336h}$  and  $C_{max}$  increased in an approximately dose-proportional manner over the range of 30 to 150 mg after both the first and last dose. Accumulation ratios for  $C_{max}$  and  $AUC_{0-336h}$  pooled across doses were 1.86 and 1.81, respectively, but steady state was not achieved after 3 doses administered Q2W.

Treatment-induced and/or treatment-boosted ADAs were detected in less participants in the 150 mg cohort (57.1%) compared to the 30 mg and 75 mg cohorts (100% and 87.5%). In general, there was a trend for a lower ADA incidence with increasing SAR442970 doses.

Total TNF showed a similar concentration increase over a few weeks following SAR442970 administration in all cohorts, reflecting target occupancy. At 150 mg Q2W the increase lasted longer, and higher concentrations were reached. All but one sample analyzed had OX40 concentrations below the LLOQ of 200 pg/mL.

Overall, this study identified no meaningful safety or tolerability concerns and provided PK and PD data to support the dose selection for the Phase 2 ACT16852 study.

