### **10.8.2 United States (US)**

At the Week 20 visit, all participants in the US will be assessed for response defined as  $\geq 50\%$  reduction from Baseline in the total AN count, with no increase from Baseline in abscess or draining tunnel count. Participants who meet the definition of response will continue in the open-label period to receive SAR442970 150 mg Q2W up to the Week 26 visit. Thereafter, responders will move to Period C which will commence with an end of treatment visit (approximately 2 weeks after the last IMP administration) and after 8 weeks conclude with an EOS Visit. Participants who do not meet the definition of response at the Week 20 visit will immediately begin Period C. The Week 20 visit will be the EOT visit for non-responders (SAR442970 will not be administered at this visit), and the EOS visit will be scheduled approximately 8 weeks after the EOT visit.

All participants in the US who complete the Week 4, Week 8, Week 12, Week 20, and Week 24 visit will have a complete physical examination at these visits. All participants in the US who complete the Week 4, Week 12, Week 20, and Week 24 visit will have laboratory testing at these visits. For details, please refer to [Section 1.3.2](#).

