2.8.2 Immunogenicity analyses

Antidrug antibodies were assessed at baseline (before first IMP administration), Week 2, Week 4, Week 16, Week 28/EOT or premature and at EOS (Week 36 or 8 weeks after premature EOT).

A 3-tiered approach will be employed to generate titer data. Serum samples will be screened for antibodies binding to SAR442970 and the titer of confirmed positive samples will be reported as a quantitative variable.

Incidence will be provided for the following ADA response categories:

- Participants with **pre-existing ADAs** correspond to participants with ADAs present in samples drawn before first administration of intervention. Participants with missing ADA sample at baseline will be considered as without pre-existing ADA.
- Participants with **treatment-emergent ADA** correspond to participants with at least one treatment-induced/boosted ADA.
 - Participants with **treatment-induced ADAs** correspond to participants with ADAs that developed at any time after first IMP administration and without pre-existing ADA (including participants without pre-treatment samples).
 - Participants with **treatment-boosted ADAs** correspond to participants with pre-existing ADAs that are boosted at any time after first IMP administration to a significant higher titer than the baseline. A 3-fold serial dilution schema is used during titration, so at least a 9-fold increase will be considered as significant.
- Participants with **unclassified ADA** correspond to participants with pre-existing ADAs that cannot be classified as treatment-boosted ADA because of missing titer(s) (i.e., a positive ADA sample at any time after first IMP administration in a participant with pre-existing ADA but with missing titer at this sample or at baseline).
- Participants **without treatment-emergent ADA** correspond to participants without treatment-induced/boosted ADA and without any inconclusive sample nor unclassified ADA at any time after first IMP administration.

- Participants **with inconclusive ADA** are defined as participants which cannot irrefutably be classified as with or without treatment-emergent ADA.

Summary of ADA at baseline, listing of participants with treatment-emergent ADA and summary table of incidence will be provided for each SAR442970 related ADA variables on the ADA population. A summary of ADA at baseline and at each visit during the treatment-emergent period (including follow-up) might be provided depending on ADA incidence.

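### Date-only windows in SAP Table 15 label the off-drug end-of-study PK and serum PD samples of US Week 20 non-responders, and of some other Period B early stoppers, as Week 28

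*SAP*

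**What the plan says.** SAP 4.4 makes the date the only criterion for by-visit allocation: "A measurement (scheduled or unscheduled) will be used if it is available and measurement date is within the analysis window". If several samples fall in one window, the one nearest the target day is taken. "Table 15 - Analysis windows for pharmacokinetics/pharmacodynamics variables" gives Week 28 a target of Period B Day 85 and a window of Days 71 to 112 for PK, ADA and PD biomarkers. Week 36 has target Day 141 and takes everything after Day 112. Period B Day 1 is the first open-label dose. Neither the table nor its footnotes consider time since last dose or an early EOS.

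The protocol synopsis gives US participants a different course: "Non-responders at Week 20 will move directly to the safety follow-up period (Period C) with the Week 20 visit serving as their EOT visit". It adds: "No IMP will be administered to non-responders at their EOT visit at Week 20". Section 10.8.2 says that "the EOS visit will be scheduled approximately 8 weeks after the EOT visit". The Brief summary says: "For US participants who are non-responders at the Week 20 assessment, the study duration will be 28 weeks". The US flowchart (Protocol 1.3.2) schedules serum PK and serum PD samples at both EOT and EOS.

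Elsewhere the SAP keeps EOS apart from Week 28. Section 2.8.2 lists ADA sampling at "Week 28/EOT or premature and at EOS (Week 36 or 8 weeks after premature EOT"). Section 2.8.3 equates Week 28 with EOT and Week 36 with EOS for serum PD.

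**The concern.** The Table 15 windows fit the 28-week course and make no provision for the US early exit, which is built into the design. An off-drug follow-up sample can therefore carry the label of an on-treatment time point.

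Serum concentration throughout the study is a secondary endpoint. SAP 2.8.3.1.1 also names the change in sTNF and sOX40L from Week 16 to Week 28, and from Week 16 to Week 36, as outputs. The protocol reports that total TNF rises under SAR442970 and reflects target occupancy. Washout samples filed as Week 28 would therefore be expected to distort that change, and the Week 36 follow-up summary would lose the same participants.

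**Working it through.** **1. Reproduce the plan's day numbers.** Period B day = (week − 16) × 7 + 1. This gives Week 18 = 15, Week 20 = 29, Week 28 = 85 and Week 36 = 141, as in Table 15. Study duration for a US non-responder is 20 + 8 = 28 weeks, as the Brief summary states.

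**2. Place the EOS visit.** EOT is Day 29, so EOS is nominally 29 + 56 = Day 85, exactly the Week 28 target. With visit tolerances (Weeks 16 and 20 at ±3 days, EOS at ±5 days), in study days:
- Earliest: Week 20 on Day 138, EOS 51 days later on Day 189, first open-label dose on Day 116. Period B day = 189 − 116 + 1 = 74.
- Latest: Week 20 on Day 144, EOS 61 days later on Day 205, first open-label dose on Day 110. Period B day = 205 − 110 + 1 = 96.

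Days 74 to 96 lie wholly inside 71 to 112, so the sample is never Week 36. These participants have no scheduled sample nearer Day 85, so the nearest-to-target rule does not displace it.

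**3. Time since last dose.** With no dose at the Week 20 EOT, the last dose is at Week 18 (Period B Day 15). The gap is 85 − 15 = 70 days, or 10 weeks (range 59 to 81 days). A completer's Week 28 sample is nominally 14 days after the Week 26 dose; with ±3 days on each visit, 8 to 20 days.

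Footnote w of the US flowchart places the last dose at the participant's own EOT visit, which would make the gap 56 days. That conflicts with the synopsis and 10.8.2, and the passages must be reconciled. The label is wrong under either reading.

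**4. Residual drug.** Protocol 2.2.1.2.1 gives a repeated-dose half-life "ranging from 170 to 212 hours (7 to 9 days"), that is 170/24 = 7.08 and 212/24 = 8.83 days. Assuming first-order decay, relative to the same participant's level 14 days after the last dose:
- 70-day gap: 2^−(56/7.08) = 0.0042 and 2^−(56/8.83) = 0.0123, so about 0.4% to 1.2%.
- 56-day gap: 2^−(42/7.08) = 0.016 and 2^−(42/8.83) = 0.037, so about 1.6% to 3.7%.

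**5. Effect on a Week 28 mean.** Let f be the share of such samples at Week 28 (not in the documents, so assumed) and r the residual ratio from the 70-day gap, with levels otherwise equal. The arithmetic mean is multiplied by 1 − f(1 − r); the geometric mean by r^f if the values are quantifiable.

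| f (assumed) | Arithmetic mean × | Geometric mean ×, if quantifiable |
|---|---|---|
| 5% | 0.950–0.951 | 0.760–0.803 |
| 10% | 0.900–0.901 | 0.578–0.644 |
| 20% | 0.801–0.802 | 0.334–0.415 |

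Under SAP 2.8.1, concentrations under the cut-off appear to count as zero in the mean but as missing in the geometric mean. In that case the geometric mean would not fall at all. No LLOQ for the PK assay is given.

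**6. Others affected.** Any participant whose EOT falls on Period B Days 71 − 56 = 15 to 112 − 56 = 56 has a nominal EOS inside the Week 28 window.

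**7. Look for a rule that prevents it.** The Period B safety and PK populations include these participants. The on-treatment restriction in SAP 2.7.3.1 covers quantitative laboratory, vital-sign and ECG summaries only. SAP 2.8.1 to 2.8.3 contain nothing equivalent.

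**The case against.** The case for treating this as minor has real force, and most of it stands.

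- **PK.** Concentrations are reported at selected time points that SAP 2.8.1 does not list, so Week 28 is presumed. Cmax, half-life and AUC come from a population PK model, with actual sampling times recorded (Protocol 8.5), so the windows do not define them. The median and an individual listing are also planned.
- **ADA.** The planned outputs are a baseline summary, a listing and participant-level incidence, which windows do not change. The by-visit table is optional. A sample 70 days after the last dose is within the 75-day treatment-emergent period, so only its label would be wrong.
- **sOX40L.** In the first-in-human study, values were below the 200 pg/mL LLOQ in the single-dose part, and all but one were in the multiple-dose part. Imputed at LLOQ/2, on-drug and washout values would be the same.
- **Size.** The share is unknown. SAP 4.3 lists the US among 15 countries, and 20% of 80 samples would already mean 16 such participants.

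These points limit the reach and size of the error. They do not remove the conflict between Table 15 and SAP 2.8.2 and 2.8.3, or its effect on the named sTNF output.

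**Conclusion.** The rule gives a wrong label as written. A US Week 20 non-responder's EOS sample, and that of a Period B stopper with EOT on about Days 15 to 56, is filed as Week 28 although it is a follow-up sample. Affected outputs are the descriptive Week 28 concentrations, if reported, the Week 16-to-28 change in sTNF (and in sOX40L where quantifiable), and the Week 36 summary, which loses these participants. By-visit ADA is affected only if that table is produced.

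The residual level of 0.4% to 1.2% rests on a 10-week gap and healthy-volunteer half-lives. The 5% to 20% fall in the arithmetic mean rests on assumed shares.

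A reader might go further in three ways that the documents do not support:
- That the misfiled samples all come from non-responders, so that the error is tied purely to response. Other Period B stoppers are caught as well.
- That Week 28 is the only concentration after Week 20 in completers. PK is also drawn at EOS, so it is only the last on-treatment one.
- That exposure parameters, ADA incidence or efficacy are biased. Population PK and participant-level incidence do not rest on these windows, and HS clinical parameters are not collected at EOS.

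**What to change.** In SAP 4.4 and Table 15, add a step before the day windows: PK, ADA and serum PD samples from the EOS visit, or otherwise taken after EOT, go to an EOS / follow-up category by nominal visit. As a back-up where the nominal visit is unclear, use more than 21 days since the last IMP. That limit lies above the 8 to 20 days possible for an on-schedule Week 28 sample and below the 59 to 81 days of the misfiled ones.

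Apply the same step in Period A. The Week 16 window opens on Day 99, so an early stopper with EOT on or after Day 99 − 56 = 43 has a nominal EOS on or after its opening. The window closes at the first open-label dose, which a participant who never enters Period B does not have.

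Do not simply limit Week 28 to the SAP's on-treatment period. It ends 14 days after the last dose, so valid Week 28 samples taken on days 15 to 20 within tolerance would be dropped.

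Separately, reconcile US footnote w with the synopsis and Protocol 10.8.2.

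The cost is a sentence or two of SAP text and minor programming. Slightly fewer observations carry the Week 28 label; no data are lost, and no new samples are needed.
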